429 Patient and parents are informed of the MRI findings and the following treatment (operative or non-
430 operative) by the PI.

431 **6.3.5 Operative treatment**

432 If the MRI cannot be completed for any reason, the images are insufficient in establishing fracture
433 pattern or if the MRI shows an unstable fracture which is displaced more than 2 mm, we will suggest
434 operative treatment with Kirschner wire fixation. Further participation in this project will be terminated.

435 **6.3.6 Non-operative treatment**

436 Patients with undisplaced and minimally displaced LHCF as seen on MRI will follow a non-operative
 437 treatment protocol (appendix 1). The treatment consists of an above elbow splint until radiographic
 438 union. Radiographic union usually occurs after four weeks; however, treatment will be continued until
 439 callus formation is seen at the cortex of the metaphysis.

440
 441 Fractures that are not complete (e.g., do not traverse both metaphysis, physis, epiphysis and joint
 442 cartilage) are considered stable. Complete fractures displaced <2 mm are considered unstable but still
 443 eligible for non-operative treatment. All patients will be seen for FU as outlined in section 6.2.

444
 445 Any patient with a fracture seen to displace more than 2 mm during FU will be suggested operative
 446 treatment.

447 **7 Definitions of outcome measures and study variables**

448 **7.1 Primary outcome**

449 **7.1.1 Mayo Elbow Performance Score (MEPS)**

450 MEPS consists of four domains; pain, elbow range of motion (ROM), stability and function [35]. We use
 451 a modified MEPS which omits the functional domain because it is not relevant in smaller children. The
 452 total score ranges from 0-100 with higher scores indicating better function (figure 5). If the total score
 453 ranges between 75 and 100, the result is good (satisfactory); 50–74, fair (acceptable); <50, poor
 454 (unsatisfactory) [36]. MEPS has been found to be accurate and reliable compared to other elbow
 455 scoring systems [37].

Criteria	No. of points
PAIN (max., 60 points)	
None	60
Mild to occasional, no medication	40
Moderate to occasional, activity limited, medication	20
Severe to incapacitating	0
MOTION (max. 30 points)	
Arc of extension/flexion:	
>90	30
60–89	20
30–59	10
<30	0
STABILITY (max., 10 points)	
Effect on function of the elbow	
None or mild (does not limit activity)	10
Moderate (impairs certain functions)	5
Severe (markedly limits activity)	0

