456 **Figure 5 - Modified Mayo Elbow Performance Score.**
 457

458

459 **7.2 Secondary outcomes**

460 **7.2.1 MRI results**

- 461 • Proportion of successful MRIs defined as a completed scan with an image quality that is useful for
- 462 analysis by the radiologist.
- 463 • MRI findings.
- 464 • Song classification based on MRI.
- 465 • Scan length (minutes).
- 466 • Any discomforts for the child during the scan.

467 **7.2.2 Radiographic results**

468 Injury radiographs and subsequent radiographs during FU will be read and described by a senior
 469 orthopedic surgeon.

470 **7.2.3 Secondary displacement**

471 Any secondary displacement and amount of radiographic displacement (mm) is recorded.

472 **7.2.4 Pain**

473 To quantify pain in the patient, an age appropriate rating scale is applied:

- 474 • Age <5 years: Face, Legs, Activity, Cry, Consolability Scale (FLACC)
- 475 • Age >4 years: Faces Pain Scale – Revised (FPS-R)
- 476 • Age >8 years: Visual analogue scale

477 **Face, Legs, Activity, Cry, Consolability Scale (FLACC)**

479 To quantify pain behaviors in children who may not be able to verbalize the presence or severity of pain
 480 FLACC [38] provides a simple framework. The child is observed for at least 2-5 minutes. Legs and body
 481 are observed uncovered. Activity is observed and body is assessed for tenseness and tone.

482

Behavior	0	1	2
Face	No particular expression or smile	Occasional grimace or frown, withdrawn, disinterested	Frequent to constant quivering chin, clenched jaw
Legs	Normal position or relaxed	Uneasy, restless, tense	Kicking or legs drawn up
Activity	Lying quietly, normal position, moves easily	Squirming, shifting, back and forth, tense	Arched, rigid or jerking
Cry	No cry (awake or asleep)	Moans or whimpers; occasional complaint	Crying steadily, screams, sobs, frequent complaints
Consolability	Content, relaxed	Reassured by touching, hugging or being talked to, distractible	Difficult to console or comfort

483

484 Assessment of Behavioural Score:

- 485 • 0 = Relaxed and comfortable
- 486 • 1-3 = Mild discomfort
- 487 • 4-6 = Moderate pain
- 488 • 7-10 = Severe discomfort/pain

489

[figure not shown]
490

491

492

493 Faces Pain Scale – Revised (FPS-R)

494 The Faces Pain Scale – Revised (FPS-R) [39] is used to quantify pain in children above four years of
 495 age. It is a self-report measure of pain intensity developed for children. It was adapted from the Faces

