- 540 • Continuous variables will be summarized using the mean, standard deviation (SD), median, inter-
541 quartile range, and minimum and maximum values and, if appropriate, according to clinically relevant
542 categories.

543

544 In general, continuous variables with both baseline and FU measurements available will also be
545 summarized in terms of the individual patient-level changes between baseline and follow-up.

546

547 A p-value of <0.05 is regarded as being significant. Data will be analyzed using SPSS (SPSS, Chicago,
548 IL, USA).

549 8.3.1 Patient discontinuation

550

551 If a participant chooses to discontinue the follow-up examinations for any reason, the date and reason
552 for drop-out is recorded and the latest examination will be carried forward in the analysis. In case of
553 drop-out before the first follow-up visit the participant will be excluded from the analysis. Participants are
only removed from the study if they decline participation.

554 9 Bias

555

556 We strive to minimize bias in our study. Minimally displaced fractures of the elbow can go unnoticed and
557 be missed by our project. However, Danish parents are usually not withholding in taking an injured child
558 to the ED. A strict protocol for referrals for treatment are in place in Denmark. All eligible patients
559 referred to Herlev and Gentofte University Hospital will be asked to participate in the study. We
560 speculate that by enrolling 50 participants the cohort will be representative of the background
561 population. We speculate that these efforts will limit selection bias. Efforts described in the follow-up
562 section reduce the risk of loss to follow-up. Overall, we find a low risk of bias in our study for the chosen
study design and size.

563 10 Benefits

564 Classifying lateral condyle fractures and establishing whether they are stable or not is the key to
565 choosing the right treatment strategy. MRI is the only feasible image modality that can make that
566 distinction.

567
568 LHCF is currently a fracture that requires open surgery in most cases due to the radiographic inability to
569 distinguish stable injuries from unstable. This project seeks to use MRI without sedation or GA in order
570 to distinguish fracture patterns. MRI has been shown to be feasible in all age groups without the need
571 for sedation or GA [24].

572
573 Thévenin-Lemoine et.al. found that 25 of 27 children could successfully complete an MRI without

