574 sedation or GA [23]. Of the 25 children, 17 (68%) had incomplete stable fracture patterns and six (24%)
575 had complete but minimally displaced fractures. In all, 23 (92%) children could be treated non-
576 operatively. Two children had unstable and displaced fractures and underwent surgery.

577
578 If proven safe and feasible, non-operative treatment for undisplaced and minimally displaced LHCF
579 would relieve the child of hospital admission, anesthesia and surgery and reduce parent's need for time
580 off work and reduce overall healthcare costs.

581
582 The investigators suspect a significant decrease in the need for operative management based on the
583 results of this project.

584 11 Risk analysis

585 The risks that occur in this study are associated with the general risks of non-operative treatment for
586 LHCF.

587 11.1 Treatment-related risks

588 Discomforts/risks from casting:

- 589 • Heat injury
- 590 • Pressure sores and skin breakdown
- 591 • Dermatitis
- 592 • Joint stiffness

593 11.2 Study disadvantages

594 Extra visits to the outpatient clinic. We follow all patients with seven visits to the outpatient clinic. This is
595 four more than with standard treatment and might be viewed as a disadvantage.

596 11.3 Study-related risks

597 11.3.1 Secondary displacement

598 During non-operative treatment of fractures, the risk of secondary displacement is well known. The risk
599 of secondary displacement of an initially undisplaced LHCF varies from 4% to more than 40%
600 depending on the initial stability and displacement [12]. As the initial stability in this study is evaluated by
601 MRI the investigators suspect that the risk of secondary displacement will be close to 4%.

602 **11.3.2 Radiation**

603 In comparison with the standard follow up of LHCF there are four additional visits to the out-patient clinic
604 with radiographs of the elbow in AP, ML and IO view. Collectively, the effective dosage is 0.004 mSv -
605 far below 0.1 mSv and is considered insignificant.

606 **11.3.3 Loss of privacy**

607 Patients' private and confidential medical information may get disclosed and confidentiality broken.
608

609 **11.4 Actions to minimize increased risks**

610 General treatment-related risks will be present whether the patient participates in the study or not. Such
611 risks will be managed by use of standards of treatment, i.e. casting by trained physicians and nurses.
612

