723 international orthopedic journal, and the results will be presented at national and international scientific
724 meetings. Reporting will adhere to the STROBE guidelines for cohort studies [31].

725 19 Termination criteria

726 The progress of the study, in particular the enrollment and safety aspects, will be closely monitored
727 together with the sponsor. The sponsor may decide to terminate the. In case of an early study
728 termination, all patients already enrolled in the study will be followed up until the last FU visit as defined
729 in the CIP.

730 19.1 Stopping rules

731 The recruitment will be put on hold for safety reason if:

732

- 733 • Secondary displacement of more than 2 mm during FU in > 75% of cases at interim analysis.

734

735 In such a case, the reported complication will be discussed with the sponsor. The sponsor will decide
736 about the actions to be taken and if the study needs to be stopped or not.

737 20 Deviations from the Clinical Investigation Plan

738 Deviations from the procedures as described in this CIP or altering the CIP without following a defined
739 process are not permitted.

740

741 A CIP deviation is any non-adherence to the protocol that does not involve the inclusion/exclusion
742 criteria, primary efficacy variable, and GCP guidelines. CIP deviations are minor and do not impact the
743 study in a major way. CIP deviations are to be reported to the sponsor within ten working days.

744

745 A CIP violation is any significant divergence from the protocol on the part of the patient, investigator,
746 sponsor, or any other responsible party that affects e.g. the inclusion/exclusion criteria, primary efficacy
747 variable, or GCP guidelines. Violations will be recorded at the study site and in the eCRF.

748 21 Amendments to the Clinical Investigation Plan

749 No changes to the approved CIP are allowed, except when the change removes immediate threats for
750 the patient safety or is of a purely administrative or logistic nature.

751

752 Should there be any need during the performance of the study to change this CIP, an amendment will
753 be developed, issued and approved by or notified to the required bodies.

754

755

756

757 22 Time schedule

Ethics Committee approvals	28.06.2021	to	01.09.2021
First patient/first visit	01.10.2021		
Last patient/first visit	01.10.2023		
Last patient/last visit	01.10.2025		
Data analysis	01.11.2025	to	01.03.2026
Final Study Report	01.03.2026	to	01.06.2026

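### The recruitment-hold rule in 19.1 counts displacement over undefined cases with stable and unstable fractures pooled, which adds to the main fault of a 75% limit: displacement of every Song stage 3 fracture would not trigger it

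*Protocol*

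**What the plan says.** Section 19.1 (Stopping rules) gives one numerical criterion for a recruitment hold: "Secondary displacement of more than 2 mm during FU in > 75% of cases at interim analysis". If it is met, the matter is discussed with the sponsor, who decides whether the study stops. The section does not say which children are the cases, does not mention fracture stage, and does not give the size or time of the interim analysis. Section 13 states that adverse events are not collected, so this is the only numerical safety trigger in the protocol text.

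Other sections separate two risk groups:

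- Section 4.4 describes stages 1 and 2 as stable and stage 3 as always unstable.
- Section 6.3.6 keeps part of the unstable group in the treated cohort: "Complete fractures displaced <2 mm are considered unstable but still" eligible for non-operative treatment.
- Section 11.3.1 says the risk "of secondary displacement of an initially undisplaced LHCF varies from 4% to more than 40" percent, depending on initial stability and displacement. The investigators expect a rate close to 4%, because stability is judged by MRI.
- Section 6.2.5 adds a control MRI for unstable stage 3 fractures only.
- Section 7.2.1 records the "Song classification based on MRI", and section 7.2.3 records any secondary displacement in mm.

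The only case mix in the protocol is in section 10, from a cited series in which "25 of 27 children could successfully complete an MRI without" sedation or anaesthesia. Of those 25, 17 had incomplete stable fractures and 6 had complete but minimally displaced ones, so 23 could be treated non-operatively. "Two children had unstable and displaced fractures and underwent surgery".

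**The concern.** The hypothesis covers stages 1, 2 and 3, but section 4.4 traces the treatment controversy to radiographs failing to separate stages 1 and 2 from stage 3. Stage 3 is therefore the group for which a safety rule matters most. A single proportion over all treated children lets the stable majority dilute what happens in that minority. Recruitment of children with stage 3 fractures could continue under 19.1 while most or all of those fractures displaced. A modest pooled rate could also not be told apart from a low risk in everyone.

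**Working it through.** **Reproducing the protocol's figures.** 17/25 = 68%, 6/25 = 24% and 23/25 = 92%, all as printed in section 10. The 75% limit and the enrolment of 50 have no stated derivation to reproduce.

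**Inputs.** The share of complete (stage 3) fractures among treated children is s = 6/23 = 0.261, exact (Clopper-Pearson) 95% CI 0.102 to 0.484. The displacement rate in stable fractures is assumed to be 4%; section 11.3.1 gives this as the bottom of the range and as the expected rate for the whole cohort, not for stable fractures alone. The stage 3 rate p3 is varied. The interim size is not stated, so 6 stage 3 + 17 stable children are used for illustration.

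**Pooled rate** = s × p3 + (1 − s) × p(stable).

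- All stage 3 displace: 0.261 + 0.739 × 0.04 = 0.290. With 0% or 10% in stable fractures it is 0.261 or 0.335.
- All stage 3 displace, share at its upper confidence limit: 0.484 + 0.516 × 0.04 = 0.505.
- Stable rate also needed to reach 75%: (0.75 − 0.261)/0.739 = 0.66.
- 40% of stage 3 displace: 0.261 × 0.40 + 0.739 × 0.04 = 0.134.

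In the 6 + 17 example, more than 75% means 18 or more of 23. Even with all 6 stage 3 fractures displaced, 12 of the 17 stable ones would have to displace as well.

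**Chance of a hold.** The pooled count is the sum of Bin(6, p3) and Bin(17, 0.04); the stage 3 count is Bin(6, p3). All limits other than 75% are illustrative.

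| True stage 3 rate | Pooled >10% (≥3 of 23) | Pooled >15% (≥4) | Pooled >20% (≥5) | Stage 3 alone, >20% (≥2 of 6) |
|---|---|---|---|---|
| 4% | 0.06 | 0.01 | 0.002 | 0.02 |
| 10% | 0.13 | 0.04 | 0.01 | 0.11 |
| 20% | 0.29 | 0.11 | 0.03 | 0.34 |
| 40% | 0.64 | 0.37 | 0.16 | 0.77 |
| 100% | 1.00 | 1.00 | 1.00 | 1.00 |

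If the case mix is left random, total stage 3 failure triggers pooled limits of 10% to 20% with probability 0.78 to 0.99 at 25 children and 0.90 to 1.00 at 50.

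**The 75% level by itself.** Counting stage 3 alone but keeping >75% needs 5 or more of 6, which has probability 0.04 at a true 40%. If every child had a true rate of 40%, so that pooling diluted nothing, the rule would trigger with probability 0.0003 at 25 children (19 or more).

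**The case against.** A reader might infer that pooling would hide total failure of stage 3 at most other limits too, or that the denominator fault would be just as serious once the limit was lowered. The figures do not support this. In the 6 + 17 example, total stage 3 failure gives at least 6 events and crosses every pooled limit from 10% to 20% with certainty. Much of the gap between 0.16 and 0.77 at a true 40% comes from applying the same 20% limit to both rules; a pooled 10% limit reaches 0.64. The level of the limit is therefore the larger fault.

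The stage 3 count is also not free of chance holds. The 0.02 belongs to a true rate of 4%, the bottom of the protocol's range. At 10% and 20% it is 0.11 and 0.34, close to the pooled >10% rule (0.13 and 0.29).

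Other safeguards exist: the control MRI for stage 3, the individual offer of surgery when displacement exceeds 2 mm (section 6.3.6), and general monitoring under section 19, where the sponsor may end the study whatever 19.1 says. They lessen the harm, but none supplies a trigger specific to stage 3.

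Finally, the inputs are thin: one small series, an assumed rate in stable fractures, and an undefined term whose pooled meaning is the plain reading, not a stated rule.

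What remains is that the rule as written cannot respond to failure in the group at risk, and that pooling costs detection of partial failure. In the example the stage 3 count does better than the pooled >10% rule on both sides: 0.77 against 0.64 at a true 40%, and 0.02 against 0.06 at 4%.

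**Conclusion.** The point holds in a limited form. On the plain reading of 19.1 and the protocol's only case mix, displacement of every stage 3 fracture gives about 29% pooled, and about 50% at the upper confidence limit of the stage 3 share, so a >75% rule would not trigger. The main fault is the 75% level; pooling adds to it. With a lower pooled limit, total stage 3 failure would usually be caught, but a 40% stage 3 rate is diluted to about 13% and detected with probability 0.64, 0.37 or 0.16 at pooled limits of 10%, 15% or 20%, against 0.77 for 2 or more of 6 in stage 3 alone.

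This rests on the 26% share from one cited series, the assumed 4% in stable fractures, and an assumed interim size of 23. The failure at 75% survives the uncertainty in the share. The detection figures are illustrative and would change with the interim size. The rule should be changed, and the change is cheap.

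**What to change.** In section 19.1, define cases as the children treated non-operatively. Count displacement separately for stage 3 and for stages 1-2, by stage on the initial MRI, each with its own denominator. The sponsor sets a limit for each count and reconciles it with the range of 4% to more than 40% in section 11.3.1; either count triggers the hold and the discussion. Both parts are needed, because splitting the count does not repair the 75% level. No particular limit is proposed here.

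The cost is protocol wording, since MRI stage and displacement are already recorded. The downside is that the stage 3 count rests on few children, so holds at moderate true rates are not rare (2 or more of 6: 0.02 at 4%, 0.11 at 10%, 0.34 at 20%), and a second trigger for stages 1-2 would add some more. Under 19.1 a hold leads only to a pause and a discussion with the sponsor.
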